##### **Aim 1: To Assess Preliminary Effectiveness via Target Engagement of Social Salience.**

Hyp 1.1. Adults with ASD in the EXP group will demonstrate significantly faster growth in IMF (primary DV), CMF (secondary DV) or WMS-F (secondary DV) than adults with ASD in the WLC group, verifying the intervention had predicted effect on the target.

**Statistical Analysis:** IMF is the primary DV because it uses the same procedure, stimuli, and metric that was used with our previous successful efficacy demonstrations of SENSE Theatre. The CMF and WMS-F are measures of the same constructs on which SENSE Theatre had effects in children and adolescents, but are measured with procedures appropriate for adults. Thus, the latter two variables are considered secondary. The effect on the primary and secondary dependent variables will be tested in separate analyses for posttest and follow-up measures. In each analysis, we will use multiple linear regression in which group (experimental = EXP or waitlist control = WLC) is analyzed as the dummy-coded independent variable, and the baseline (pre-intervention) variable is analyzed as a covariate (assuming homogeneity of slopes assumption is met). By including the baseline value as a covariate, the coefficient for group becomes the between-group (EXP vs. WLC) difference in the pre-test adjusted posttest (or follow-up) scores (i.e., a measure of change similar to residualized gain scores). This method is often superior to a method that uses raw change scores directly because it improves the statistical power of the significance test and improves the accuracy of effect size estimates relative to between-group differences in raw change scores . If significant difference between groups are detected on other baseline variables that correlate with the outcome, those baseline variables will also be controlled in the multiple linear regression model, assuming appropriate assumptions are met. We will assess the homogeneity of slopes assumption by testing the interaction effect between baseline variable and treatment group assignment. If there is a significant interaction, then we will assess the treatment effect at various levels of the pre-intervention variable. If other regression assumptions (e.g., homoscedasticity, normality of residuals) are not met, robust standard error estimates will be used to test parameters in analogous models.

**Power analyses for tests of hypothesis associated with Aim 1.** Using a one-tailed test (based on the a priori predicted direction of differences), 80% power, 5% type 1 error, and a post-attrition sample size with equal groups of 40 (20 in each group), the minimal detectable effect size is an  $R^2$  of 0.14 (i.e., standardized mean difference of .80). The effect size of the between-group difference on the pretest-adjusted posttest ERP measure of memory for faces in our most recent RCT of SENSE Theatre was an  $R^2$  of .18 (i.e., standardized mean difference of .94). Therefore, it is feasible that we will detect the predicted SENSE Theatre effect on our primary measure of memory for faces with the proposed sample size.

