##### **Aim 2: Test the Link Between the Degree of Target Engagement (Social Salience), Social Interaction, Anxiety/Depression (STAI, ABCL, CDI) and Functional Outcomes of Social Skills (SRS, ABAS).**

Hyp 2.1: Adults in the EXP group will demonstrate significantly more growth on functional outcomes.

Hyp 2.2: There will be a positive association between (a) memory for faces (IMF, CMF or WMS-F) at post-test or follow-up and (b) social skills (CASS involvement and rapport) at posttest or follow-up.

Hyp 2.3: There will be a negative association between (a) memory for faces (IMF, CMF or WMS-F) at post-test or follow-up and social awareness symptoms (SRS-2 awareness T score), or anxiety/depression (STAI, ABCL, CDI) at posttest or follow-up.

**Statistical Analysis:** The aforementioned statistical analyses in Hyp 1.1 will be followed for Hyp 2.1 with the functional outcomes as the dependent variable. The SRS-2 is the instrument from which we will derive our primary DV because it is the same instrument we have used to show the association between our primary measure of memory for faces and social symptoms in our past work on children and adolescents with ASD. From the SRS-2, the Awareness subscale and its T score will be the subscale and score type used to test this aim because this is the variable that correlates with the primary measure of memory for faces (i.e., the ERP measure). The other measures are secondary DVs because, while they measure similar or identical constructs as those for which SENSE Theatre has had effects in children and adolescents, but these are measured with procedures appropriate for adults in the present proposal. In two separate analysis (one for posttest and one for follow-up), we will examine the association of memory for faces with the primary functional outcome measure using linear regression. We will also explore how changes in social awareness symptoms are related to changes in memory for faces by modeling the social awareness outcomes for all timepoints as a function of the change in memory for faces and a timepoint dummy variable using a generalized estimating equation. To assess the effect of change in memory for faces on change in social awareness symptoms we will test the change in memory for faces by timepoint interaction. Similar analyses will be conducted for secondary DVs.

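### Hyp 1.1 labels IMF primary but, as worded, lets any of three measures at either of two visits verify target engagement; the SAP should name the one test that decides

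*SAP*

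**What the plan says.** SAP section 4.4, Aim 1, Hyp 1.1 predicts "significantly faster growth in IMF (primary DV), CMF (secondary DV) or WMS-F (secondary DV) than adults with ASD in the WLC group". The same sentence gives the consequence of a significant result: "verifying the intervention had predicted effect on the target". The statistical analysis paragraph below it explains why IMF is primary and the other two measures secondary. It then provides for separate baseline-adjusted regressions at posttest and at follow-up, without naming a primary visit.

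The Aim 1 power paragraph works from "Using a one-tailed test (based on the a priori predicted direction of differences), 80% power, 5% type 1 error" with 20 participants per group. It reports a minimal detectable effect of R² 0.14 ("i.e., standardized mean difference of .80"). Feasibility is argued from an earlier trial's effect on the ERP face-memory measure at posttest, R² 0.18 ("i.e., standardized mean difference of .94").

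The interpretative-framework paragraph at the end of the Aim 2 material says that alpha will not be adjusted, because adjustment would raise Type II error. It acknowledges that type 1 error is inflated by several tests of one aim and says the results will therefore be regarded as pilot. The next paragraph says the results will help inform Go/No-Go decisions on further development or testing. No Go/No-Go criterion is given.

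**The concern.** The three measures are joined by *or*, and verification is attached to the whole disjunction. Nothing in the section restricts verification to IMF. A significant result on CMF or WMS-F at follow-up, with IMF null at both visits, would meet the hypothesis as written. The primary label is explained but is given no stated role in deciding whether the target was engaged.

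Target engagement is the first aim, and its results feed the Go/No-Go decision. If the intervention had no effect on any of the three measures, the written criterion would still be met more often than a single test at the level used in the power calculation would suggest. The SAP tells the reader that inflation exists, but not how large it is or which result to rely on.

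**Working it through.** **Inputs from the SAP.** One-tailed 5% per test, 80% power and 20 per group (Aim 1 power paragraph); three measures and two visits (Hyp 1.1 and its analysis paragraph); no alpha adjustment (interpretative-framework paragraph).

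**Assumption.** The correlation among the six test statistics is not given. It is varied from 0 to 0.9.

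**Step 1: reproduce the plan's figure.** For one baseline-adjusted comparison, df = 40 − 3 = 37 and the one-tailed critical value is 1.687. The noncentrality is d·√(n/2) = 0.80 × √10 = 2.53. Power by the noncentral t is 0.799, and the effect giving exactly 80% power is d = 0.801. R² = d²/(d² + 4) = 0.64/4.64 = 0.138. The stated 0.80 and 0.14 are reproduced. A two-sided 5% test does not fit (power 0.69, minimal d 0.91). The stated 5% is therefore the level of one one-tailed test.

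**Step 2: count the routes.** 3 measures × 2 visits = 6 tests.

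**Step 3: chance of at least one false positive in six, with no effect on any measure.**

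- Independent tests: 1 − 0.95⁶ = 1 − 0.735 = 26.5%.
- Equally correlated tests: the probability that the largest of six standard normal statistics exceeds 1.645, from 1,000,000 simulated draws per setting:

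| Correlation | At least one of six |
|---|---|
| 0 | 26.5% |
| 0.3 | 22.0% |
| 0.5 | 18.6% |
| 0.7 | 14.7% |
| 0.8 | 12.6% |
| 0.9 | 10.0% |

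- Structured case, with correlation 0.5-0.8 between visits for one measure and 0.3-0.5 between measures at one visit: 17-22%.
- Check by simulating the planned type of regression at N = 40 (15,000 trials per setting): 26.5% with independent tests and 18-22% with correlated ones. Each single test rejected about 5% of the time.

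**Step 4: treat the primary label as binding, with the visit still open.** IMF at either visit gives 1 − 0.95² = 9.75% if independent, 8.8% at correlation 0.5 and 6.8% at 0.9.

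**Step 5: compare remedies.**

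| Rule | False verification | Minimal detectable d for IMF | Power for IMF at d = 0.94 |
|---|---|---|---|
| IMF at posttest decides | 5.0% | 0.80 | 90% |
| Bonferroni over six (0.05/6 = 0.0083 each) | at most 5% | 1.06 | 68% |

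The SAP's objection on Type II error is well founded against the second rule. It does not touch IMF under the first.

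**The case against.** The strongest reply is that the SAP has already dealt with this. It has a paragraph on unadjusted multiple testing, admits the inflation, and downgrades the results to pilot. That stands, and the point is not one of concealment. What the paragraph leaves open is the size of the inflation and which test decides.

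A reader might infer that the SAP promises 5% for the whole any-of-six criterion and contradicts itself. The documents do not support that. The phrase "80% power, 5% type 1 error" is an input to one power calculation, whose conclusion concerns the primary face-memory measure, and no passage claims 5% for the family.

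It can also be said that Hyp 1.1 is a research hypothesis and not a decision rule, and that its primary and secondary labels give IMF precedence. That is a fair reading, and it reduces the figure to about 7-10%. It does not reach 5%, because the visit is still not named.

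The link to Go/No-Go is loose. The SAP sets no any-of-six trigger, and Future Directions makes use of the data for a larger trial depend on engagement that is also linked to clinically meaningful functional outcomes. One false positive would therefore not launch a larger trial by itself.

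A reader might also extend the point to Hyp 2.3, which lists alternatives in a similar way. That does not carry over. Hyp 2.3 attaches no verification to a significant result, and Aim 2 names SRS-2 Awareness as its primary outcome and powers its association with memory for faces.

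Finally, restricting verification to IMF has a cost. The SAP describes CMF and WMS-F as using procedures suited to adults, and an effect seen only there would no longer verify engagement. This is a real but small loss for the aim. It is not a loss of power for IMF.

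**Conclusion.** The point holds as a defect of wording. As written, Hyp 1.1 allows verification on a secondary measure, at either visit, with the primary null. The chance of at least one false verification over six tests is 26% if independent, 19% at correlation 0.5, 15% at 0.7 and 10% at 0.9. These figures assume no effect on any measure and one-tailed 5% per test.

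The independent case is an upper reference and not a realistic value, since the same participants are measured at both visits. The documents give no correlations, so no single figure can be claimed. A reader who lets the IMF label govern faces about 7-10%. The SAP's pilot caveat is genuine, but it sits poorly beside the language of verification and does not identify a deciding test.

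**What to change.** In Hyp 1.1, state that target engagement is verified only by IMF at posttest, tested one-tailed at 5%. This is the measure and visit on which the Aim 1 feasibility argument rests, so it follows the SAP's own choice of primary measure. State that IMF at follow-up, and CMF and WMS-F at both visits, are supportive: reported unadjusted with confidence intervals, and unable on their own to verify engagement.

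The cost is a change of SAP wording. Sample size, visits and alpha stay as they are, and the minimal detectable effect for IMF remains 0.80. The one downside is that a positive secondary measure with a null IMF can no longer be called verification. It can still be reported as a supportive finding.

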- **Follow-up (2.5 months after post visit)**
 - **Assessment (1-2 hours)**
 - **ERP (45 minutes)**
 - **Contextual Assessment of Social Skills (30 minutes)**

RECRUITMENT

EVENTS

- Regional autism community outreach groups (i.e. [Autism Tennessee](#) Conference)
- State Autism Speaks Walk
- Find other events, possible sources of recruitment using regional support groups and awareness programs
Recruitment Resources
- Research Site Website: Coordinate Links and Information with PI and site information technology department

MAINTAINING RECRUITMENT

- Maintain ongoing list of interested participants and of peers/counselors.

INCLUSION/EXCLUSION CRITERIA

- Must have an autism spectrum disorder (score ≥ 7 on ADOS)
- An estimated scale IQ score on the WASI or WAIS of ≥ 70
- Baseline threshold score of ≥ 10 on either the Cambridge Face Memory Test or Wechsler Memory for Faces Test
- No medication restriction—although note these during the phone screen in addition to any other medical psychological diagnoses/conditions—could be exclusionary.
- Must communicate using complete sentences/have fluent speech.

- **• Siblings should not be in the same cohort**
- **Aggression: During phone screen, ask if there a history of current or recent aggression**
- *If in doubt about any of these factors, consult with [name].

ID CONVENTION

- The ID system is STA; start with 101 for cohort 1, 201 for cohort 2, etc.
 - For example, STA 101, STA 201, etc.

SCHEDULING PARTICIPANTS

IMPORTANT POINTS TO MAKE

- Studying peer-mediated effects on social cognition, communication, and interaction through the SENSE Theatre® program. Assignment to the experimental group (SENSE Theatre®) or waitlist control (WLC) will be randomly assigned.
- Visits required: initial eligibility visit, then **pre-treatment, mid-point of treatment, post-treatment, and a 2 1/2-month follow up.**
- Autism
- Ages 18-40
- Visit breakdown
 - Eligibility: Assessment (about 2-3 hrs.)
 - Diagnostic evaluation (ADOS, ask if completed within last 2 years)
 - Estimated IQ (WASI within last year?)
 - Pre-visit:
 - Assessment (about 1 hour)—self-report forms and social perception measures
 - Cambridge Face Memory Test (CFMT)
 - Wechsler Memory for Faces (WMS-F III)
 - Computer Memory for Faces
 - CASS (about 30 Minutes)
 - Interaction in study offices
 - Two 3-minute interactions with two different adults
 - Videotaped to analyze later
 - ERP
 - 30 minutes

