****All forms must be completed by same rater in Pre, Post, and Follow-up (i.e. same family member/informant)! ****

SATISTACTION SURVEY

- At the conclusion of each cohort, send an email to all participants in the cohort (in both the EXP and WLC groups) who have completed the SENSE Theatre® intervention program, including the performances, requesting them to fill out a Satisfaction Survey that will be used to help improve future programs. The email will include a link to the online REDCap survey. For participants who wish to complete a paper copy of the Satisfaction Survey, mail those participants printed PDFs of the REDCap survey and ask them to complete and return.

SENSE THEATRE® INTERVENTION PREPARATION

GROUP ASSIGNMENT

- Once randomization into SENSE Theatre® or WLC is complete and participants have been assigned to groups, send letters to participants informing them to which group they have been assigned.
- Send out RedCap survey which collects information regarding Medication (see if there have been any changes), food allergies, behavioral information, t-shirt size (for SENSE Theatre®).
- Add participant and research helper contacts to a designated lab cell phone if applicable

PEERS/COUNSELORS

- **Application:** Interested peers and counselors will complete an application
- **Decisions:** Principal investigator and theatre director will narrow down who is to be interviewed for a peer and counselor position.
- **Background checks:** if required
- **Protection of Minors Training:** Make sure all counselors and peers are compliant with the site's requirements for protections of minors training. Contact site IRB for "Research Involving Minors" for more information pertinent to site requirements.
- **Consent and Video Release Forms:** sent to peers/counselors participating in intervention.
- **Intervention Information:** Send training schedule, location map, and first days schedule (via email), and an email reminder 1 week before training begins.

TRAINING

SPEAKERS

- PI will be responsible for contacting and choosing speakers.
- For SENSE Theatre® peer training, coordinate who will be presenting when, 6 weeks before intervention begins.
 - Research Assistant/Coordinator—"Introduction to Autism"
 - Confidentiality & Code of Conduct, SENSE Theatre® Manual, SENSE Lab & Theatre, Behavioral Strategies.
- Copies of past presentations can be provided to any sites by the SENSE Research Coordinator.

BINDERS

- Binder Materials (SENSE Theatre®):

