#### 4.4. Statistical Design and Power

**Post-attrition Sample Size Used to Test Aims and Compute Statistical Power.** We propose to recruit approximately 46 participants to enroll 40 participants over the first 2 years of the project with the last year being used to complete the treatment and assessment for the last wave of recruitment. Using a 10% attrition rate, which is the maximum attrition rate to date of past SENSE Theatre trials, the post-attrition sample size will be 40 (equally distributed between experimental and control groups). The analyses and power analyses are based on post-attrition sample size and past findings involving the primary dependent variables.

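### If randomisation was blocked by cohort, the planned regression leaves the block out and reports a standard error slightly too large; one conditional sentence corrects this

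*SAP*

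**What the plan says.** SAP 4.4, Aim 1, Statistical Analysis, fits a linear regression in which group "is analyzed as the dummy-coded independent variable, and the baseline (pre-intervention) variable is analyzed as a covariate". Further covariates enter by one rule: "If significant difference between groups are detected on other baseline variables that correlate with the outcome, those baseline variables will also be controlled". The same model serves the functional outcomes: "The aforementioned statistical analyses in Hyp 1.1 will be followed for Hyp 2.1 with the functional outcomes as the dependent variable". No SAP text supplied names cohort.

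The protocol runs in cohorts. Under ID Convention, participant numbers "start with 101 for cohort 1, 201 for cohort 2, etc". The inclusion criteria keep siblings out of the same cohort. The satisfaction survey instruction reads "At the conclusion of each cohort, send an email to all participants in the cohort (in both the EXP and WLC groups", so a cohort holds both arms. SAP 4.4 describes enrolment "over the first 2 years of the project with the last year being used to complete the treatment and assessment for the last wave".

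On how allocation was done, the text is thin. The protocol says assignment is random. Its Group Assignment section takes over once randomisation to the programme "or WLC is complete and participants have been assigned to groups, send letters to participants informing them to which group they have been assigned", without describing blocks. The SAP's only statement on balance is overall: "the post-attrition sample size will be 40 (equally distributed between experimental and control groups".

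**The concern.** If each cohort was randomised as a block, the arms are balanced within cohort by design. A model without the block leaves differences between cohorts in the residual, although they largely cancel from the group comparison. The reported standard error is then too large and the test rejects less often than its nominal 5%.

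The SAP's covariate rule does not repair this. It is triggered by a difference between arms, which is what blocking prevents, so a balanced cohort factor stays out however strongly it predicts outcome. At stake is a little power in a trial of 20 per arm, where the SAP itself justifies baseline adjustment partly by power and declines alpha adjustment to avoid Type II error.

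**Working it through.** **1. The plan's own figure.** Inputs from SAP 4.4, Aim 1 power analysis: 20 per arm, one-tailed 5%, 80% power. The noncentrality is d × √(n/2) = 0.80 × √10 = 2.53, with 40 − 3 = 37 df. Power is 79.9% and the detectable effect is d = 0.801. R² = d²/(d² + 4) = 0.64/4.64 = 0.138. The stated 0.80 and 0.14 reproduce. For the earlier trial's d = 0.94, R² = 0.8836/4.8836 = 0.181, against the stated .18.

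**2. Would the covariate rule pick up cohort?** A chi-square test of arm by cohort gives p = 1.0 for exactly balanced tables and 0.75 to 0.93 for near-balanced ones (for example 10/9 against 10/11, or 4/5/5/6 against 6/5/5/4). It would not.

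**3. Reported against true standard error.** The documents give neither the number of cohorts nor the variance between them. Assume K cohorts and a share v of baseline-adjusted residual variance lying between cohorts, common to both arms. With balance within cohort, the true SD of the group estimate is about √[(1 − v) × 2/20]: 0.300 at v = 10% and 0.283 at v = 20%. Simulation, K = 4, 12,000 trials, without/with the cohort term:

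| v | Mean reported SE | Actual SD of estimate |
|---|---|---|
| 10% | 0.3147 / 0.3020 | 0.3012 / 0.3008 |
| 20% | 0.3109 / 0.2845 | 0.2886 / 0.2879 |

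Without the term the reported SE is too large by 0.3147/0.3012 − 1 = 4.5% and 0.3109/0.2886 − 1 = 7.7%. The actual SD hardly moves.

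**4. Power.** Outcome = d × group + 0.7 × baseline + cohort effect + error, with residual SD 1, cohort effects random with variance v and error variance 1 − v. Arms are balanced within near-equal cohorts; 37 df without cohort, 38 − K with; 40,000 trials per cell. Power (%) at d = 0.80, without/with cohort:

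| K | v = 0 | v = 10% | v = 20% |
|---|---|---|---|
| 2 | 78.6 / 78.6 | 81.7 / 82.9 | 83.5 / 86.0 |
| 3 | 79.2 / 79.1 | 80.8 / 82.5 | 82.5 / 86.0 |
| 4 | 79.0 / 78.8 | 80.8 / 82.5 | 82.8 / 86.5 |
| 5 | 79.1 / 78.8 | 80.6 / 82.3 | 82.4 / 86.3 |
| 6 | 78.8 / 78.5 | 80.9 / 82.6 | 81.9 / 85.9 |

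A separate run (K = 2 to 5, 12,000 trials) covers smaller shares: +0.1 to +0.2 points at v = 2% and +0.5 to +0.8 at v = 5%. At d = 0.94 with K = 4, power is 89.1/89.0, 90.5/91.6 and 92.0/94.0 at v = 0, 10% and 20%.

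**5. Type 1 error of the planned test** (K = 2, 4, 6; 40,000 trials): 4.3-4.4% at v = 10% and 3.6-4.2% at v = 20%; with cohort, 4.9-5.1%. An independent run with K = 4 gives 4.5% and 3.7% without the term.

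**6. Imperfect balance.** With 46 allocated within cohort and 6 lost at random (K = 2, 4, 6), the term costs 0.3, 0.6 and 1.1 points at v = 0. It gains 1.3 to 1.5 at 10% and 2.4 to 3.9 at 20%. With six cohorts of odd and even sizes and no attrition, the cost at v = 0 is 0.9 points (78.8/77.9).

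**7. If arms were balanced only overall.** For K = 2, 3, 4, 5, 6, the term costs 1.0, 2.4, 3.3, 4.1 and 5.5 points at v = 0. At v = 10% the change is +0.7, +0.5, −0.2, −1.2 and −2.4. Only at v = 20% does it gain throughout (K = 2: 82.6/85.5; K = 6: 79.7/81.2).

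**The case against.** The premise is not in the documents. Both arms would normally appear in each cohort under simple randomisation or a single overall list too, so the survey instruction is weak evidence of blocking. Since part of the SAP was not available, blocking and its handling may be described there. This stands: the point must remain conditional, and nothing here shows an omission from the full plan.

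The variance between cohorts is also assumed. Nothing in the documents says that cohorts differ in both arms alike after baseline adjustment, and the baseline covariate would take up stable differences in level. At a share of 2% the gain is negligible. This stands too, and is why ranges are shown.

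Four stronger readings are tempting and not supported:

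- *The omission biases the effect or inflates false positives.* It does neither; the test errs towards conservatism.
- *The term makes the estimate more precise.* Under balance the sampling SD is essentially the same with and without it. Only the reported SE changes.
- *The trial falls short of its stated power.* In the within-cohort simulations the planned model has 78.6 to 79.2% at v = 0, where the term does not help, and 80.6 to 83.5% at v = 10% and 20%.
- *The term deals with clustering in the theatre groups.* The waitlist arm receives the programme only after all study visits, so shared delivery acts on EXP alone. In a simulation of EXP-only cohort effects (K = 4), type 1 error was 6.6% without and 6.9% with the term at v = 10%, and 8.8% and 9.1% at 20%.

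Finally, the SAP calls its results pilot. A test run at about 4.3% instead of 5%, without bias, is unlikely to change a Go/No-Go decision. That limits the priority but does not remove the point, because the correction is nearly free.

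**Conclusion.** A small, conditional point, optional to act on. It holds if randomisation was blocked within cohort and cohorts differ in a way common to both arms. Then the standard error reported for the group effect, in Aim 1 and in its reuse for Hyp 2.1, is somewhat too large. The one-tailed 5% test runs at about 4.3-4.5% with 10% cohort variance and 3.6-4.2% with 20%. Including the block restores the nominal level and adds about 0.5-0.8 points of power at 5% cohort variance, 1-2 at 10% and 2.5-4 at 20%. The number of cohorts and these variance shares are assumptions.

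A reader might infer that cohort should be adjusted for in any event. The figures do not support that: if arms were balanced only overall, the term can cost more power than it returns.

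**What to change.** Check the randomisation record. Then add to the Aim 1 Statistical Analysis in SAP 4.4, before outcome data are examined:

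> *Where randomisation was blocked within cohort, the cohort (randomisation block) is included as a fixed categorical factor in every model that estimates the group effect, whether or not it differs between arms.*

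This also covers Hyp 2.1. If allocation was not blocked by cohort, leave the model as stated. Avoid a general rule for pooling small cohorts, which would depart from the blocks and add discretion; at most, pool a cohort left with only one arm after attrition.

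Cost: one sentence and no new data, since the cohort is already coded in the participant ID. The term uses 1 to 5 degrees of freedom with 2 to 6 cohorts, and loses up to about 1 point of power if cohort explains nothing. Clustering within EXP would need separate treatment.

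### If the slopes test is significant, the single Aim 1 group comparison gives way to effects at unspecified baseline levels, and the SAP does not say which result decides the hypothesis

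*SAP*

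**What the plan says.** SAP section 4.4, Aim 1, Hyp 1.1 (Statistical Analysis) specifies a linear regression of each outcome on a group indicator, in which "the baseline (pre-intervention) variable is analyzed as a covariate (assuming homogeneity of slopes assumption is met"). The condition is checked by testing the group-by-baseline interaction. If that test is significant, the plan changes: "If there is a significant interaction, then we will assess the treatment effect at various levels of the pre-intervention variable".

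The rule applies to each of IMF (primary), CMF and WMS-F (secondary), analysed separately at posttest and follow-up. The Aim 2 text carries the same analysis over to the functional outcomes of Hyp 2.1.

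The Aim 1 power paragraph sets the intended error rate: "Using a one-tailed test (based on the a priori predicted direction of differences"), with "80% power, 5% type 1 error" and "a post-attrition sample size with equal groups of 40 (20 in each group"). The analysis paragraph itself gives no sidedness.

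The paragraph on multiple testing, after the Aim 2 power statement, declines alpha adjustment, acknowledges inflated type I error and calls the results pilot. The text then says that the results will inform Go/No-Go decisions.

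**The concern.** The group comparison is a single defined test only while the preliminary interaction test is non-significant. In the other branch several conditional effects take its place. The SAP leaves open:

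- the significance level of the interaction test;
- how many baseline levels are examined, and where;
- whether there is any adjustment across levels;
- which result supports or fails to support the hypothesis.

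The levels could thus be chosen after the data are seen, and a significant effect at one of them could be read as target engagement. A chance interaction makes this likely: when the fitted lines diverge, the estimated group difference is large at one end of the baseline range even if there is no effect anywhere.

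At stake is the meaning of the 5% in the power statement for the primary IMF comparison. So is a single overall effect per outcome that can be set beside the standardized differences of .80 and .94 in the power paragraph and used to plan a larger trial.

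**Working it through.** **Inputs from the SAP.** 20 analysed per group, one-tailed 5%, 80% power, minimal detectable "standardized mean difference of .80" (R² 0.14).

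**Assumptions, because the SAP is silent.** Interaction tested at two-sided 5% (10% as sensitivity); two to five baseline levels or a fine grid; no adjustment across levels; any significant level counts as a positive. Data are normal with baseline-outcome correlation 0.5 (0 and 0.8 also tried).

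**Step 1: the plan's own figure.** For equal groups R² = d²/(d² + 4) = 0.64/4.64 = 0.138, which rounds to the stated 0.14. The exact one-tailed power at d = 0.80 with 20 per group is 0.799. A two-sided test would have power 0.693. The stated figure therefore reproduces, and it refers to one one-tailed 5% test.

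**Step 2: the two-stage rule under the null.** Trials were simulated with no group effect and no true interaction, 200,000 per scenario. If the interaction was not significant, the group test from the model with group and baseline was used. If it was significant, the group effect was tested at each chosen level.

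False-positive rate of the whole procedure, one outcome at one time point, interaction tested at 5%:

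| Baseline levels examined | One-tailed 5% | Two-sided 5% |
|---|---|---|
| Only the mean-baseline effect decides | 5.0–5.1% | 5.0–5.1% |
| −1, +1 SD | 7.4% | 8.2% |
| −1, 0, +1 SD | 7.3% | 8.1% |
| −1.5, 0, +1.5 SD | 8.3% | 9.0% |
| −2, −1, 0, +1, +2 SD | 8.9% | 9.5% |
| 41-point grid over ±2 SD | 8.8% | 9.3% |

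Repeat runs of the one-tailed rule gave 7.3–7.5% for mean and ±1 SD, and 8.7–8.9% for five levels. With the interaction tested at 10%, the range over these sets of levels is about 8.8–11.0% one-tailed and 9.6–11.2% two-sided.

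**Step 3: where the excess comes from.** About 5% of null trials have a significant interaction by chance. Among those, at least one level is significant (one-tailed) in about 53% with three levels and 82% with five. Combining the branches:

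- three levels: 0.95 × 0.049 + 0.05 × 0.53 = 0.047 + 0.027 ≈ 0.073;
- five levels: 0.95 × 0.050 + 0.05 × 0.82 = 0.048 + 0.041 ≈ 0.089.

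**Step 4: sensitivity.** With mean and ±1 SD, one-tailed, the rate is 7.4% at correlation 0 or 0.8, and 7.4–7.5% with 18 or 23 per group. Correlation and attrition hardly matter; the unstated decision rule does.

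**Step 5: one fixed test.** Always using the group test from the model with group and baseline gives 4.9–5.1%. With randomisation and equal groups, that coefficient targets the average effect whether or not the slopes differ, so unequal slopes do not force the main test to be abandoned.

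**The case against.** The strongest reply is that the excess rests on a rule the SAP does not contain. The SAP says only that effects at several levels will be assessed, not that one significant level establishes Hyp 1.1. That is correct. A reader might infer that the plan as written has a 7–9% error rate, but the documents do not support so firm a statement: if the mean-baseline effect decides, the rate stays at about 5%.

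The upper figures also need unadjusted tests at ±2 SD. With 20 per group, only about 20 × 0.023 ≈ 0.5 participants per arm would lie beyond each of those points. At the more usual mean and ±1 SD the excess is about 2.4 percentage points.

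Next, the SAP openly accepts inflation. Hyp 1.1 already has six unadjusted tests (three outcomes at two time points). If independent, they would carry a family-wise rate of 1 − 0.95⁶ ≈ 26%; correlation lowers it. A few points on one comparison are small beside that. This stands as to severity. But that paragraph does not mention this source, and its reason for not adjusting, the loss of power, does not apply to a fix that leaves alpha alone. A reader can also count the declared outcomes and time points and discount for them, which is not possible for levels that are never named.

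Finally, probing a significant interaction is recognised practice, and level-specific effects can help to plan a larger trial. That supports reporting them. It does not require them to replace the overall test.

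**Conclusion.** The gap is real and is visible in the text without any simulation: after a significant slopes test, the levels, the significance level that triggers the switch and the deciding result are not pre-specified. It affects each Hyp 1.1 comparison and, by reference, Hyp 2.1.

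Its size is conditional. If any significant level counts and the interaction is tested at two-sided 5%, the one-tailed false-positive rate per outcome and time point is about 7.4% (mean and ±1 SD) to 8.9% (adding ±2 SD). Across plausible readings it runs from about 5% to about 11%.

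Two further inferences should be avoided. The 53–82% in Step 3 applies only to the roughly 5% of null trials with a chance interaction and is already contained in the overall rates; it is not an additional error. And a test at one pre-chosen level, made without the preliminary test, keeps its 5%; the excess comes from the switch combined with the choice among levels. Nothing here makes the trial invalid. For a pilot that feeds a Go/No-Go decision, this is a specification that should be tightened.

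**What to change.** For each outcome and time point, state that the group coefficient from the regression on group and baseline, without an interaction term, is the single deciding test whatever the interaction test shows. Delete the parenthetical condition in "analyzed as a covariate (assuming homogeneity of slopes assumption is met"). Report the interaction with its confidence interval, and the group effect at the mean and ±1 SD of baseline, as descriptive results that cannot by themselves establish the hypothesis.

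An acceptable alternative, if pre-specified, is the group coefficient at the overall mean baseline from the model that keeps the interaction. The SAP must say which model is meant: without an interaction term, centring baseline does not change the group coefficient, and with one it does. Apply the same wording to Hyp 2.1.

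The cost is two sentences. Alpha and sample size do not change, and no planned analysis is lost. The downside is that if the effect truly differs by baseline, a level-specific effect is reported but does not count as support for the hypothesis.
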